9.3.7 Medical History, Medications, and Non-Drug Therapies

At screening, the subject's medical history will be described for the following body systems including severity (mild, moderate, or severe as defined in Section 11.1.2.1) or surgery and start and end dates: eyes, ears, nose, and throat; respiratory; cardiovascular; gastrointestinal; musculoskeletal; neurological; endocrine; hematopoietic/lymphatic; dermatological; and genitourinary.

All medications taken and non-drug therapies received within the 14 days prior to product administration until completion/termination will be recorded on the concomitant medications and non-drug therapies CRFs.

Pregnant women will be followed for one year post-treatment for any evidence of teratogenicity, birth defects and other congenital complications in their offspring.

9.3.8 Physical Examinations

At screening, if an abnormal condition is detected, the condition will be described on the medical history CRF. During follow-up, if a new abnormal or worsened abnormal pre-existing condition is detected, the condition will be described on the SAE CRF. If the abnormal value was not deemed an AE because it was due to an error, due to a pre-existing disease (described in Section 11.1.1.4), not clinically significant, a symptom of a new/worsened condition already recorded as an AE, or due to another issue that will be specified, the investigator will record the justification on the source record.

9.3.9 Clinical Laboratory Parameters

Baxalta will provide the option for physicians to use a central laboratory to process, antihuman and anti-porcine FVIII antibodies, should they choose to do so. If these assessments are made, it is recommended that a Bethesda assay using the Nijmegen modification be undertaken for antibodies measurement, and that pFVIII antibodies be tested before and during treatment administration, and in the follow-up. Lab results from local or other central laboratories available in the medical chart will be recorded; it is not a requirement of the study that these lab tests be completed.

Hematology

Laboratory parameters may include Hematology parameters (hemoglobin, hematocrit, red blood cell count, white blood cell count with differential, platelet count), and will be documented in the CRFs if collected in regular clinical practice.

9.3.10 Vital Signs

Vital signs will include height (cm) and weight (kg), and will be reported at enrollment, and whenever else as available in the medical records as close to the time of Obizur dosing as possible. Vital signs will be recorded on the CRF.

9.3.11 Subject Completion/Discontinuation

A subject is considered to have completed the study when he/she ceases active participation in the study because the subject has, or is presumed to have, completed the study according to the protocol.

Reasons for completion/discontinuation will be reported on the Completion/ Discontinuation CRF, including: completed, screen failure, AE (e.g., death), discontinuation by subject (e.g., lost to follow-up, dropout), study terminated by the MAH, or other (reason to be specified by the investigator). Regardless of the reason, all data available for the subject up to the time of completion/discontinuation should be recorded on the appropriate CRF and will be used in the analysis and included in the study report.

In the event of subject discontinuation due to an AE, clinical and/or laboratory investigations performed as part of the evaluation of the event will be reported to the MAH. Details of the outcome may be reported to the appropriate regulatory authorities by the responsible party.

9.4 Data Sources

Investigators (or clinical staff trained for data entry) will enter data required by the protocol into the EDC system; all data shall be transcribed within 14 days of entry into the patient chart. Designated staff will have access to the data entry system after they have been fully trained.

Data for entry could come from an electronic medical chart, a paper chart or from laboratory forms. It is expected that the majority of the data will be obtained from hematology departments in hospitals; however, there is potential that other sources of documentation may be used. Source type will be captured in the CRF.

Validation programs will be designed to check for data discrepancies. Data will be reviewed for completeness and accuracy; any necessary data changes will be communicated to the clinical site.

Post-electronic data entry, MedDRA coding will be conducted for all medical conditions reported and WHODRUG coding for all reported medications.

9.4.1 Source Data

Source data are defined as all information in original records and certified copies of original records of clinical findings, observations, or other activities that are necessary for the reconstruction and evaluation of the trial. Source data are contained in source documents (original records or certified copies), which may be in paper and/or electronic format. Source data for this study comprise the following: hospital records, medical records, clinical and office charts, laboratory notes, pharmacy dispensing records, recorded data from automated instruments, subject files, and records kept at the pharmacy, at the laboratories, and at medico-technical departments involved in the study.

Data will be extracted from existing patient medical charts; all data shall be transcribed into the EDC system within 14 days of entry into the patient chart. Post-electronic data entry, MedDRA coding will be conducted for all medical conditions (including medical history) reported and WHODRUG coding for all reported medications.

9.5 Study Size

There will be one prospective cohort of approximately 40 patients with AHA who have had a bleeding episode and are being treated with Obizur prospectively. This sample size of 40 will be adequate to assess the number of therapy-related safety events experienced by this group of Obizur-treated AHA patients. In the event that some data from the retrospective group are assessed with the prospective cohort, (raising the total number of evaluable patients from 40 to 50), the following 95% confidence intervals (CIs) would be obtained.

The following calculations were completed to assess the two-sided 95% CIs around the proportion of subjects experiencing a true safety event in this population being treated with Obizur; the exact (Clopper-Pearson) method was used for calculation. These confidence limits are defined for the proportion (number of subjects with an event divided by the number of treated subjects) only. For the gray highlighted areas below, assuming 5% of subjects experience a related safety event within the population of AHA patients administered Obizur, a sample size of 40 subjects yields a two-sided 95% CI of (0.6%, 16.9%) and a sample size of 50 persons yields a two-sided 95% CI of (0.8%, 15.1%).

	Actual Width ^a	Proportion (P) ^b	95 % CI ^c Lower Limit ^d	95% CI ^c Upper Limit ^e
40 Subjects	10.7%	1%	0.0%	10.7%
	13.8%	3%	0.1%	13.9%
	16.3%	5%	0.6%	16.9%
	18.4%	7%	1.3%	19.7%
	20.9%	10%	2.7%	23.7%
	24.1%	15%	5.7%	29.8%
50 Subjects	9.0%	1%	0.0%	9.0%
	12.0%	3%	0.2%	12.2%
	14.3%	5%	0.8%	15.2%
	16.2%	7%	1.7%	17.9%
	18.5%	10%	3.3%	21.8%
	21.5%	15%	6.4%	27.9%

Actual Width: Value of the distance from the lower limit to the upper limit of the 95% CI. Width if P = 0.5 is the maximum width for a confidence interval with the given sample size.

b Proportion (P): Proportion of the sample assumed to have the outcome (i.e., SAE).

^c Confidence level = 0.95.

d Lower Limit (lower limit of the 95% CI).

^e Upper Limit (upper limit of the 95% CI).

9.6 Data Management

9.6.1 Data Collection Methods

The investigator will maintain complete and accurate paper format study documentation in a separate file. Study documentation may include information defined as "source data" (see Section 9.4.1) records detailing the progress of the study for each subject, signed ICFs, correspondence with the Ethics Committee (EC) and the study monitor/MAH, enrollment and screening information, CRFs, SAE reports (SAERs), laboratory reports (if applicable), subject diaries (if used), and data clarifications requested by the MAH.

The investigator will comply with the procedures for data recording and reporting. Any corrections to paper study documentation must be performed as follows: (1) the first entry will be crossed out entirely, remaining legible; and (2) each correction must be dated and initialed by the person correcting the entry; the use of correction fluid and erasing are prohibited.

The investigator is responsible for the procurement of data and for the quality of data recorded on the CRFs. CRFs will be provided in electronic form.

If electronic format CRFs are provided by the MAH, only authorized study site personnel will record or change data on the CRFs. If data are not entered on the CRFs during the study visit, the data will be recorded on paper and this documentation will be considered source documentation. Changes to a CRF will require documentation of the reason for each change. An identical (electronic/paper) version of the complete set of CRFs for each subject will remain in the investigator file at the study site.

The handling of data by the MAH, including data quality assurance, will comply with regulatory guidelines and the standard operating procedures of the MAH. Data management and control processes specific to the study will be described in the data management plan (see Section 14.1).

9.6.2 Software

The software for data management will be determined by the CRO conducting the study.

All computations and generation of tables, listings, and data for figures will be performed using SAS® version 9.4 or higher (SAS Institute, Cary, NC, USA), or a comparable statistical software.

9.7 Data Analysis

9.7.1 Datasets and Analysis Cohorts

All treated subjects will be included in the analysis dataset.

9.7.2 Handling of Missing, Unused, and Spurious Data

Analyses will be performed using available data, because, due to the non-interventional nature of the study, missing values are expected. There will be no imputation. All reasonable attempts should be made by the site to limit the amount of missing data.

9.7.3 Methods of Analysis

The analysis plan will be fully described in a written and approved SAP. Briefly, descriptive statistics will include specifically but not exclusively, arithmetic mean, medians, standard deviations, minimum, maximum, proportions, frequency counts, 25th and 75th percentiles, and 95% confidence intervals of select point estimates. Figures will be prepared to illustrate patterns of data over time where appropriate. Analyses will be performed using available data (missing values are expected due to the non-interventional nature of the study).

Therapy-related SAEs will be described in listings and tables and will presented by MedDRA system organ class (SOC) and preferred term (PT) and incidence rates will be calculated. Incidence will be interpreted as incidence proportion (number of patients with events/number of patients treated) and incidence rate (xx events per xx year of follow-up). Tables outlining the hemostatic effectiveness and immunogenicity of Obizur, frequency, total dose, total number of infusions of Obizur required to control bleeding episodes will be developed. Tables displaying concomitant medications and patient comorbidities will also be created. Time from symptoms to diagnosis to treatment will be reported. Where feasible, analyses may be performed within meaningful subgroups.

9.7.3.1 Primary Outcome

The primary outcome (see Section 9.1.1) is patient safety in terms of AEs, their seriousness and severity. In particular, describing:

• Incidence of therapy-related SAEs and level of severity

These data will be described in tables and listings.

9.7.3.2 Secondary Outcomes

The secondary outcomes will be descriptive in nature.

Secondary outcomes will describe effectiveness of Obizur as measured by:

- Effectiveness assessment for resolution of bleeding, determined as either bleeding stopped or didn't stop.
 - ➤ If bleeding did not stop, a reason should be provided (e.g., death)
- Time to bleeding resolution, death, or switch to another treatment.
- Number of Obizur units/kg required for control of bleeding (bleeding stopped)
- Number of Obizur infusions required for control of bleeding (bleeding stopped)
- Newly recognised anti-pFVIII inhibitors or increase in titer of anti-pFVIII inhibitors from pre-treatment level, impact on hemostatic efficacy and associated clinical manifestations if any, and evolution of titer over time
- Occurrence of hypersensitivity reactions
- Occurrence of any thrombogenic event

9.7.4 Planned Interim Analysis of the Study

Annual study report updates will be completed, which will include basic demographic and safety information. Complete information on these reports will be outlines in the SAP. No formal interim analyses are planned for this study.

9.8 Quality Control

Examples for quality control and quality assurance planning and implementation for the construction of the analytical data and the analysis of data are detailed in CDER's Manual of Policy and Procedures (MAPP) 6700.2 Standards for Data Management and Analytic Processes in the Office of Surveillance and Epidemiology (OSE), (FDA MAPP 6700.2).

9.8.1 Investigator's Responsibility

The Investigator will comply with the protocol (which has been approved/given favorable opinion by the competent/health authority and/or EC, as applicable), and applicable regulatory requirements as described in the Non-interventional Trial Agreement.

http://www.fda.gov/AboutFDA/CentersOffices/CDER/ManualofPoliciesProcedures/default.htm#ODS

The Investigator is ultimately responsible for the conduct of all aspects of the study at the study site and verifies by signature the integrity of all data transmitted to the MAH. The term "Investigator" as used in this protocol as well as in other study documents, refers to the Investigator or authorized study personnel that the Investigator has designated to perform certain duties. Sub-investigators or other authorized study personnel are eligible to sign for the Investigator, except where the Investigator's signature is specifically required.

The Investigator will retain study documentation and data (paper and electronic forms) in accordance with applicable regulatory requirements and the document and data retention policy, as described in the Non-interventional Trial Agreement.

9.8.2 Direct Access to Source Data/Documents

The Investigator/study site will cooperate and provide direct access to study documents and data, including source documentation for monitoring by the study monitor, audits by the MAH or its representatives, review by the EC, and inspections by applicable regulatory authorities, as described in the Non-interventional Trial Agreement. If contacted by an applicable regulatory authority, the investigator will notify the MAH of contact, cooperate with the authority, provide the MAH with copies of all documents received from the authority, and allow the MAH to comment on any responses, as described in the Non-interventional Trial Agreement.

9.8.3 Training

The study monitor will ensure that the Investigator and study site personnel understand all requirements of the protocol and his/her regulatory responsibilities as an investigator. Training may be provided at an investigator's meeting, at the study site, and/or by instruction manuals. In addition, the study monitor will be available for consultation with the Investigator and will serve as the liaison between the study site and the MAH.

9.8.4 Monitoring

The study monitor is responsible for ensuring and verifying that each study site conducts the study according to the protocol, standard operating procedures, other written instructions/agreements, and applicable regulatory guidelines/requirements. The investigator will permit the study monitor to visit the study site at appropriate intervals, as described in the Non-interventional Trial Agreement. Monitoring processes specific to the study will be described in the clinical monitoring plan (see Section 14.1).

9.8.5 Auditing

The MAH and/or MAH's representatives may conduct audits to evaluate study conduct and compliance with the protocol, standard operating procedures, other written instructions/agreements, and applicable regulatory guidelines/requirements. The Investigator will permit auditors to visit the study site, as described in the Non-interventional Trial Agreement. Auditing processes specific to the study will be described in the clinical quality management plan (see Section 14.1).

9.8.6 Non-Compliance with the Protocol

If monitoring and/or auditing activities identify serious and/or persistent non-compliance with the protocol, the MAH may terminate the Investigator's participation in the study.

9.9 Limitations of the Research Methods

A challenge when conducting a study among patients with a rare disease is to identify enough patients for the study. Based on the clinical trial data, there is an expectation that this is feasible.

10. PROTECTION OF HUMAN SUBJECTS

10.1 Compliance Statement

This study will be conducted in accordance with this protocol and applicable national and local requirements for good pharmacovigilance practices.

Page 40 of 49

2015 MAR 11

10.2 Subject Privacy

The investigator will comply with applicable subject privacy regulations/guidance as described in the Non-interventional Trial Agreement.

10.3 Ethics Committee(s) and Regulatory Authorities

Before enrollment of patients into this study, the protocol, ICF, any promotional material/advertisements, and any other written information to be provided will be reviewed and approved/given favorable opinion by the EC and applicable regulatory authorities. The EC's composition or a statement that the EC's composition meets applicable regulatory criteria will be documented. The study will commence only upon the MAH's receipt of approval/favorable opinion from the EC and, if required, upon the MAH's notification of applicable regulatory authority(ies) approval, as described in the Non-interventional Trial Agreement.

If the protocol or any other information given to the subject is amended, the revised documents will be reviewed and approved/given favorable opinion by the EC and relevant regulatory authorities, where applicable. The protocol amendment will only be implemented upon the MAH's receipt of approval and, if required, upon the MAH's notification of applicable regulatory authority(ies) approval.

10.4 Informed Consent

Investigators will choose patients for enrollment in consideration of the study eligibility criteria. The Investigator will exercise no selectivity so that no bias is introduced from this source.

All patients and/or their legally authorized representative must sign an ICF before entering into the study according to applicable regulatory requirements. Before use, the ICF will be reviewed by the MAH and approved by the EC and regulatory authority(ies), where applicable, (see Section 10.3). The ICF will include a comprehensive explanation of the study without any exculpatory statements, in accordance with the elements required by applicable regulatory requirements. Patients or their legally authorized representative(s) will be allowed sufficient time to consider participation in the study. By signing the informed consent form, patients or their legally authorized representative(s) agree to the use of their data for the study, unless they withdraw voluntarily or are terminated from the study for any reason.

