9.2.7 Subject Withdrawal and Discontinuation

Any subject may voluntarily withdraw (i.e., reduce the degree of participation in the study) consent for continued participation and data collection. The reason for withdrawal will be recorded on the End of Study CRF.

The data collected on withdrawn subjects will be used in the analysis and included in the non-interventional study report.

Discontinuation (i.e., complete withdrawal from study participation) may be due to dropout (i.e., active discontinuation by subject) or loss to follow-up (i.e., discontinuation by subject without notice or action). Additionally, the investigator and responsible party have the discretion to discontinue any subject from the study if, in their judgment,

continued participation would pose an unacceptable risk for the subject.

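### Section 10.4 makes permission to use data end on withdrawal or termination, while Sections 9.2.7, 9.3.11 and 9.7.1 require those patients' data in the analysis

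*Protocol*

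**What the plan says.** Four places in the protocol bear on the data of patients who leave early.

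- **Section 10.4 (Informed Consent)** describes what a signature means: patients or their representatives "agree to the use of their data for the study, unless they withdraw voluntarily or are terminated from the study for any reason".
- **Section 9.2.7 (Subject Withdrawal and Discontinuation)** describes withdrawal as concerning "consent for continued participation and data collection". It then states: "The data collected on withdrawn subjects will be used in the analysis and included in the non-interventional study report". It also lets the investigator and responsible party discontinue a subject if "continued participation would pose an unacceptable risk for the subject".
- **Section 9.3.11 (Subject Completion/Discontinuation)** lists among the reasons for ending participation "AE (e.g., death), discontinuation by subject (e.g., lost to follow-up, dropout), study terminated by the MAH". It says that, whatever the reason, available data "up to the time of completion/discontinuation should be recorded on the appropriate CRF and will be used in the analysis".
- **Section 9.7.1 (Datasets and Analysis Cohorts)**: "All treated subjects will be included in the analysis dataset".

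No section says which rule prevails.

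**The concern.** The exception in Section 10.4 attaches to the use of data, has no time limit and covers every reason for termination. Read literally, it withholds permission for the analysis that the other three sections prescribe. An analysis rule does not settle this, because consent limits which data may be analysed, and a later SAP cannot widen a consent already given.

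The primary objective (Section 8.2) is the incidence of therapy-related SAEs. Section 9.7.3 expresses it as patients with events over patients treated, and as events per follow-up time. Section 9.7.2 rules out imputation. If leavers' data could not be used, those patients would drop out of the numerator, the denominator and the follow-up time. Some reasons for leaving are safety-related, so the loss need not be random with respect to the outcome.

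**Working it through.** **1. The texts side by side**

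| Question | Section 10.4 | Sections 9.2.7, 9.3.11, 9.7.1 |
|---|---|---|
| Patient withdraws voluntarily | Agreement to data use no longer applies | Data collected are analysed and reported (9.2.7) |
| Patient is terminated or discontinued | Agreement no longer applies, whatever the reason | Data up to that time are analysed, whatever the reason (9.3.11) |
| Limit to data arising after departure | None stated | Data up to departure explicitly kept (9.3.11) |
| Analysis set | Not addressed | All treated subjects (9.7.1) |

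The first two rows conflict as written. The conflict would disappear if 10.4 were limited to data arising after departure, but 10.4 does not say so.

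**2. Can leaving be related to the outcome?** Yes. An adverse event is a listed reason in Section 9.3.11, and risk to the subject is a ground for discontinuation in Section 9.2.7.

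**3. The plan's own figure.** Section 9.5 takes N = 40, an event proportion of 5% and the exact (Clopper-Pearson) method. With x events in n patients:

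- lower limit = 0.025 quantile of Beta(x, n − x + 1)
- upper limit = 0.975 quantile of Beta(x + 1, n − x)

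Here x = 0.05 × 40 = 2 and n = 40. The limits are 0.61% and 16.92%, width 16.31%. This reproduces the protocol's 0.6% to 16.9% and width 16.3%.

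**4. Illustration of a loss.** The protocol gives no withdrawal or termination rate and no event risk among leavers. The number lost is therefore an assumption: one patient, removed from numerator and denominator.

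- The patient lost had an event: x = 2 − 1 = 1, n = 40 − 1 = 39. Estimate 1/39 = 2.6%; limits 0.06% and 13.48%, that is 0.1% to 13.5%.
- The patient lost had no event: x = 2, n = 39. Estimate 2/39 = 5.1%.

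With about two events expected, one excluded event patient roughly halves the estimate, while one excluded event-free patient barely moves it and in the opposite direction. Both the direction and the size therefore depend on who leaves.

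**The case against.** The strongest reply is that the protocol supplies its own narrower reading. Section 9.2.7 frames withdrawal as forward-looking, and the sections that specifically govern withdrawal, discontinuation and the analysis set all keep the data. On that view, 10.4 is a loose summary of what signing means, and nothing in it orders deletion or exclusion. This reading is plausible and probably what was intended. But 10.4 speaks of use, not of collection, and extends to termination for every reason. The likely intention is a reason to write the limit into 10.4; it does not make the present sentence say so.

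Two further points stand and restrict the consequence.

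- The consent form is not among the documents. Under 10.4 it is reviewed by the MAH and approved by the ethics committee separately, so its actual wording is unknown.
- Participation adds no required visits, tests or interventions (Section 9.1). Stopping Obizur because of an SAE is not leaving the study; Section 11.1.2 records it as an action taken for the event. Discontinuation because participation itself poses a risk should therefore be rare.

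A reader might infer that the plan will exclude leavers, that those leavers will mostly be patients with SAEs, or that the primary incidence will be understated by a calculable amount. The documents do not support any of these. The stated analysis rule is to include leavers, no leaving rate or event risk among them is given, and event-free leavers would push the estimate up instead.

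**Conclusion.** The point holds as an inconsistency between the consent provision and the analysis provisions. Section 10.4 does not clearly permit the analysis that Sections 9.2.7, 9.3.11 and 9.7.1 require, and the protocol does not say which governs. The textual conflict rests on no assumption.

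The consequence is conditional. Data would be lost only if the consent form carries the 10.4 wording and that wording is applied literally. The loss would lower the estimated incidence only if patients with events are over-represented among those who leave. The fall from 5.0% to 2.6% shows how sensitive a study expecting about two events is to one patient; it is not an estimate of bias. The sample size and the confidence-interval table in Section 9.5 are unaffected.

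The correction should be made because it is cheap and the measure exposed is the primary one.

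**What to change.** Reword the last sentence of Section 10.4, and the consent form if it carries the same wording, to state that:

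- data collected up to withdrawal or discontinuation are retained and analysed, in line with Sections 9.2.7 and 9.3.11;
- only further data collection stops;
- termination by the investigator or the MAH does not revoke permission to use data already collected;
- all of this is subject to applicable privacy rules and ethics committee approval.

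The cost is a sentence or two in the protocol and the consent template if done before ethics submission. Once the documents are approved, Section 10.3 requires the revised versions to go back for review. Patients who have already signed might also need to be re-consented, which may not be possible for those who have died or been lost to follow-up.
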